18.	REFERENCES	16

LIST OF ABBREVIATIONS

ACCORD	Academic and Clinical Central Office for Research & Development – Joint office for The University of Edinburgh and Lothian Health Board
CI	Chief Investigator
CONSORT	Consolidated Standards of Reporting Trials
CRF	Case Report Form
eCRF	Electronic Case Report Form
GCP	Good Clinical Practice
HAQ	Health Assessment Questionnaire
ICH	International Conference on Harmonisation
PI	Principal Investigator
PA	Paget’s Association
QA	Quality Assurance
PDB	Paget’s disease of bone
REC	Research Ethics Committee
REDCap	Research Electronic Data Capture
SF36	36-Item Short Form Survey
SOP	Standard Operating Procedure

INTRODUCTION

1.1 Background

Paget's disease of bone (PDB) is a common skeletal disorder characterised by increased bone turnover affecting one or more bones throughout the skeleton [1]. The most common symptom of PDB is bone pain which can be due to increased metabolic activity or complications such as bone deformity, secondary osteoarthritis, spinal stenosis, and pathological fractures. Many patients are asymptomatic however and treatment is not always required. Although genetic factors play an important role in PDB, environmental influences also contribute [2]. Many environmental triggers have been postulated to play a role including viral infections, calcium and vitamin D deficiency, mechanical loading, exposure to environmental toxins and changes in diet. More recently, the intestinal microbiome has been found to play a key role in regulating bone metabolism [3]. This has mostly been studied in preclinical models of postmenopausal bone loss [4], but clinical studies have also shown that administration of probiotics can modulate bone loss in postmenopausal women [5, 6]. Furthermore, it has also been shown that dietary induced modulation of the microbiome can modify bone and joint damage in an autoinflammatory disease caused by a missense mutation of *Pstpip2* in mice [7]. Taken together this raises the possibility the dietary manipulation aimed at increasing amounts of calcium in the diet or manipulating the microbiome through changes in diet or administration of probiotics could favourably influence disease activity or symptoms of disease in patients with PDB. The aim of this study is to test this hypothesis in the context of a randomised controlled trial.

1.2 Rationale for study

Epidemiological studies have shown that environmental factors influence the occurrence and severity of Paget's disease of bone, but the identity of these factors is unclear. The present study will investigate the role of dietary calcium and vitamin D and of the microbiome as environmental factors which may modify disease activity in PDB.

There is previous evidence that dietary calcium [8] and vitamin D deficiency [9] might predispose to PDB by causing secondary hyperparathyroidism which in turn would be expected to stimulate osteoclast activity and also evidence that probiotics can favourably influence bone loss in postmenopausal women [4]. The aim of this study will be to explore the effects of dietary calcium and vitamin D supplements and probiotic supplements on biochemical markers of metabolic activity in patients with mild PDB who are not considered to require treatment with bisphosphonate therapy, and to study effects on pain and quality of life.

2. STUDY OBJECTIVES

2.1 Primary objective

To evaluate the effects of dietary calcium and vitamin D supplements, probiotics and placebo on metabolic activity of PDB as assessed by changes in serum procollagen type I N propeptide (PINP)

2.2 Secondary objective

To evaluate the effects of dietary calcium and vitamin D supplements, probiotic supplements and placebo on the following clinical and biochemical variables:

- Biochemical markers of metabolic activity in PDB other than PINP

- Health related quality of life (SF36)
- The presence and severity of pain at sites affected by PDB
- The intestinal microbiome

3. STUDY DESIGN

Randomised placebo controlled multicentre trial. An overview is provided in Figure 1.

4. INTERVENTIONS

Probiotics

The probiotic intervention will consist of three lactobacillus strains in capsular form, to be taken once daily to provide 1×10^{10} PFU of lactobacillus per day for 6 months. The preparation will be supplied by Probi (www.probi.com) and is identical to a supplement previously used in the prevention of postmenopausal bone loss in women [10]. The dose is one capsule per day. The capsules are made of hydroxypropylmethyl cellulose, with titanium dioxide as a colouring agent. They contain maize starch (bulking agent), magnesium stearate (processing aid) and maltodextrin (bulking agent). The capsules will be supplied by Probi (www.probi.com).

A three month supply will be dispensed at the baseline visit, the second three month supply will be given at the 3-month study visit (Table 1). Participants will be dispensed one large box (10 x 10 tablets) and one small box (1 x 10 tablets) at the first visit. They will be dispensed a large box (10 x 10) at the second visit. They will be asked to finish the first supply before they move on to the resupply.

Placebo Probiotics

The placebo probiotics consists of identical capsules containing maize starch (bulking agent), magnesium stearate (processing aid) and maltodextrin (bulking agent). A three month supply will be dispensed at the baseline visit, the second three month supply will be dispensed at the 3-month study visit (Table 1). Participants will be dispensed one large box (10 x 10 tablets) and one small box (1 x 10 tablets) at the first visit. They will be dispensed a large box (10 x 10) at the second visit. They will be asked to finish the first supply before they move on to the resupply. The dose is one capsule per day.

The probiotic and placebo capsules will be shipped by Probi under temperature-controlled conditions (2-8°C) to the co-ordinating centre where it will be stored in a dedicated temperature-controlled refrigerator. The product will be shipped from the co-ordinating centre to study centres on an intermittent basis under temperature-controlled conditions (2-8°C) and stored in local study centres in a temperature-controlled refrigerator. The probiotic or placebo will be dispensed to participants by members of the local study team. Alternatively, and depending on local circumstances, the probiotics and placebo probiotics may instead be stored in the local hospital pharmacy and dispensed from there.

On randomisation, the local PI or delegated individual will prepare a prescription for the probiotic or placebo probiotic as appropriate. On receipt of this, a member of the local research team will dispense the appropriate number of packs to the patient.

Alternatively, if it is decided that the local pharmacy at the recruitment site will store the probiotics and placebo probiotics, these will be dispensed by the local pharmacy to the participant (or a member of the local research team) on receipt of a prescription for the probiotic or placebo probiotic.

Calcium and vitamin D

A dietary calcium and vitamin D supplement will be prescribed containing 1000 mg elemental calcium and 880 units of vitamin D in the form of AccreteD3 one a day 1000mg /880 IU chewable tablets for 6 months. Should the participant be randomised to this intervention, the calcium and vitamin D supplements will be prescribed by a member of the local study team and dispensed to participants by the local hospital pharmacy.

Table 1 summarises the number of doses of probiotics, placebo probiotics, a calcium/vitamin D supplements to be prescribed and dispensed at each visit. Copies of these prescriptions should be held in the appropriate section of the local site file.

Time-point	Probiotic dose	No. capsules	Placebo Probiotic dose	No. capsules	Calcium/Vitamin D dose	No. tablets
Baseline (0)	1 daily	120	1 daily	120	1 daily	120
3 months	1 daily	100	1 daily	100	1 daily	100

Table 1: Number of capsules to be dispensed to participants at each study visit.

Participants should be asked to return all unused study product at their final study visit. The first supply will give +/- 2 weeks window for for the 3- month visit. The resupply will allow +/- 2 weeks window for their 6-month visit.

5. ENDPOINTS

5.1 Primary endpoint

Change in metabolic activity of PDB as assessed by serum concentrations of PINP at six months

5.2 Secondary endpoints

Changes in other biochemical markers of bone metabolism including ALP, CTX, PTH and 25(OH)D

Changes in health related quality of life as assessed by SF36

Changes in the presence and severity of pain at sites affected by PDB

Changes in the microbiome as assessed by 16S sequence analysis of stool samples

6. STUDY POPULATION

6.1 Number of participants

A total of 75 patients with PDB will be studied to give 25 patients in each treatment group

6.2 Inclusion criteria

- Clinical diagnosis of PDB confirmed by characteristic appearances on radionuclide bone scan and /or x-ray
- Serum total alkaline phosphatase elevated above the upper limit of normal or within the upper half of the local reference range, or evidence of active PDB on radionuclide bone scan within the previous two years so long as the participant has not been treated with bisphosphonates or denosumab between the scan and the baseline visit

- Willing and able to give informed consent

6.3 Exclusion criteria

- Unable or unwilling to give informed consent
- Bisphosphonate therapy thought to be indicated for treatment of PDB on clinical grounds
- Currently being treated with bisphosphonates, denosumab or calcitonin for any reason
- Currently being treated with combined calcium and vitamin D supplements
- Treatment with oral or intravenous bisphosphonates during the previous 24 months
- Treatment with denosumab during the past 12 months
- Treatment with calcitonin during the previous 3 months.
- Treatment with combined calcium and vitamin D supplements during the past 4 weeks
- Receiving probiotics during the previous 3 months.

6.4 Prohibited medications and supplements

During the trial, participants will be instructed not to take calcium and/or vitamin D supplements or probiotics other than those supplied as part of the intervention

6.5 Co-enrolment

Co-enrolment will be permitted for participants who have already been enrolled in studies that involve collection of data such as questionnaires and tissue samples such as Biobank UK and similar epidemiological studies. Co-enrolment will also be permitted for individuals who are taking part in interventional studies. This will be considered on a case-by-case basis taking into account the potential impact on both studies, subject to an agreement between both groups of investigators provided that the potential burden to participants is not considered excessive.

7. PARTICIPANT SELECTION AND ENROLMENT

7.1 Identifying participants

Potential participants will be identified by their normal health care provider through review of clinic lists at the participating study centres.

7.2 Consenting participants

Participants will be approached to take part in the study by their normal health care provider and provided with an information sheet and consent form. After being given an adequate amount of time to consider whether or not to take part (typically at least 24 hours or longer) they will be invited to provide written informed consent by a suitably qualified member of the local healthcare team or research team.

7.3 Withdrawal of participants

Subjects will be informed that they have the right to withdraw from the study at any stage without having to give a reason. They will be advised that if they do withdraw it will not impact on the normal medical care they receive. If the participant does decide to withdraw from the study, two options will be given

- Complete withdrawal: No further contact from the study team and destruction of all data gathered and all samples collected up until the point of withdrawal.
- Partial withdrawal: Termination of study procedures up to the time of withdrawal with retention of samples and data up to that point. Participant consents to being contacted by study team about future studies that may be of interest.

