8.3 End of study visit (6 months)

The end of the study visit will be performed six months after commencing the supplement or placebo (with a window of 2 weeks on either side). Blood samples for biochemistry and specialised biochemistry will be repeated. The presence and severity of bone pain localised to sites affected by PDB will be recorded. Health related quality of life assessed by SF36 will be recorded. Stool samples will be collected for microbiome analysis. Any adverse events that have occurred since the last visit will be recorded. Capsule and tablet counts will be performed to assess adherence. The schedule of study assessments is summarised in Table 1.

Table 1. Schedule of study assessments

	Baseline	3 months	6 months
Medical history	X		
Current and recent drug treatments	X	X	X
Adverse events		X	X
Blood for routine biochemistry	X	X	X
Blood for routine haematology	X		
Blood for specialised biochemistry	X	X	X
Stool sample	X	X	X
SF36	X	X	X

Pain at affected site	X	X	X
Blood for genetic analysis	X		
Blood for transcriptome analysis	X		

9. Processing and analysis of samples

All samples will be labelled with a Study ID barcode. These will be supplied to sites ahead of participant recruitment. Details of the labelling system can be found in Section 11.1.

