13.2 IDENTIFYING AEs AND ARs

All AEs and ARs will be identified from the time a participant signs the consent form to take part in the study until the completion of study follow-up.

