13.3 RECORDING AEs AND ARs

All AEs, including post-operative complications, and mortality, will be recorded as part of the outcome measures in the study CRF. There is no requirement to complete an additional AE form.

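### Section 7.3 ends follow-up under both withdrawal options, and one of them destroys data already collected, adverse events included, that other sections require to be recorded and kept

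*Protocol*

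**What the plan says.** Protocol section 7.3 sets the trigger as a decision to leave the study: "If the participant does decide to withdraw from the study, two options will be given". Complete withdrawal is "No further contact from the study team and destruction of all data gathered and all samples collected up until the point of withdrawal". Partial withdrawal is "Termination of study procedures up to the time of withdrawal with retention of samples and data up to that point", coupled with agreement to be approached about later studies. No third option is listed, and no class of data is excepted from destruction.

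Four other parts of the protocol bear on this:

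- **Primary endpoint (5.1):** "Change in metabolic activity of PDB as assessed by serum concentrations of PINP at six months".
- **Six-month visit (8.3):** "The end of the study visit will be performed six months after commencing the supplement or placebo", with a two-week window on either side. At that visit, "Capsule and tablet counts will be performed to assess adherence".
- **Adverse events (13.2 and 13.3):** "All AEs and ARs will be identified from the time a participant signs the consent form to take part in the study until the completion", that is, to the end of follow-up. Also, "All AEs, including post-operative complications, and mortality, will be recorded as part of the outcome measures in the study CRF", and 13.3 asks for no separate adverse event form.
- **Retention (16.4):** all study documentation is kept for at least three years after the end of the study. Withdrawn participants are not excepted.

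**The concern.** Two things look wrong.

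First, a participant's choice made after randomisation can erase everything the trial holds on that person. The stated reason for leaving, the adverse event that may have prompted it, the baseline and 3-month PINP, and the arm to which the person was allocated all fall within the wording. If leaving is related to the product or to symptoms, the comparison of arms loses those participants and also the data needed to describe them or to test how much their loss matters. A statistical analysis plan cannot repair this, because the data no longer exist. The safety comparison is exposed in the same way.

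Second, section 7.3 is silent on the participant who no longer wants the capsules or tablets but would still give a blood sample at six months. With only two options on offer, a site may record that person as a withdrawal, and the primary endpoint is then not collected.

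**Working it through.** The point rests on the text, so the check is to set the sections side by side.

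**Step 1: who is covered.** Section 7.3 applies to a participant who decides to leave the study. It does not mention stopping the product. Section 8.3 dates the six-month visit from the start of the supplement and does not require that it is still being taken. Non-adherence is measured by counts, and no rule says that it ends participation.

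**Step 2: what survives.** Take a participant who leaves after the 3-month visit and before the 6-month visit, and read 7.3 literally.

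| Item | Complete withdrawal | Partial withdrawal | Stops product, does not withdraw |
|---|---|---|---|
| Allocation | not exempted | kept | kept |
| Baseline and 3-month PINP | destroyed | kept | kept |
| Adverse events already recorded | destroyed | kept | kept |
| Later adverse events | not collected | not collected | collected |
| 6-month PINP (primary endpoint) | not collected | not collected | collected under 8.3 |

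The last column follows from 8.3, but 7.3 does not state it as an option.

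**Step 3: where the sections collide.** Section 13.3 places adverse events in the CRF and asks for no other form, so they are part of the data gathered and fall under the destruction clause. For a complete withdrawal, a site cannot both destroy all data and meet 16.4, which retains all study documentation. Nor can the trial report every adverse event identified since consent, as 13.2 and 13.3 intend, once the CRF entries are gone.

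**Step 4: how the options are bundled.** Partial withdrawal carries agreement to later contact about other studies. A participant who wants no further contact but would leave the data in place has no matching option. The only no-contact choice is the one that destroys everything.

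**Step 5: size.** The protocol gives no withdrawal rate and no split between the two options. Only the weight of one person can be computed: sections 6.1 and 12.1 give 25 per group and 75 in total, so each participant is 1/25 = 4% of an arm and 1/75 = 1.3% of the trial. Neither section states an allowance for loss.

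**The case against.** The strongest reply is that leaving a study ordinarily means that follow-up ends, so it is no defect that both options end it. Partial withdrawal keeps all earlier data and samples, so the loss of baseline PINP, 3-month PINP and adverse events is confined to those who choose complete withdrawal. Nothing suggests how many would. Offering erasure is also a promise made to participants, and so a consent choice rather than a statistical error. Section 13.3 governs how events are recorded and says nothing about later deletion, so the sharper conflict is with 16.4. Some traces might survive locally, such as the copies of prescriptions that section 4 keeps in the site file.

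Much of this stands. The destruction problem is limited to one option, and its frequency is unknown. But a consent promise still has to agree with the rest of the protocol, and this one does not. Prescription copies hold neither PINP nor adverse events, and 7.3 does not say that they are spared.

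A reader might also infer that anyone who stops the supplement loses the primary endpoint. The protocol does not support that. Section 7.3 is triggered by leaving the study, and a participant who stops product without leaving still has the 6-month visit. What remains is an unstated option and the risk that sites treat stopping as leaving.

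**Conclusion.** The concern holds in this form. As written, 7.3 permits the destruction of all data on a randomised participant, with no exemption for adverse events, allocation or PINP. That conflicts with 13.2, 13.3 and 16.4 and allows removal from the analysis after allocation. Separately, the section fails to distinguish stopping product from leaving the study, which puts some 6-month PINP values at avoidable risk.

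The effect cannot be sized from the protocol. A reader might be tempted to assume that 10% to 20% of one arm leaves and that their PINP change differs from that of stayers by 0.5 to 1.0 SD. This gives a bias of 0.10 × 0.5 = 0.05 SD to 0.20 × 1.0 = 0.20 SD, or 8% to 33% of the 0.6 SD in section 12.1. The arithmetic is right, but both inputs are assumed and the result describes total attrition. Some of those participants would be lost under any wording, and the part due to 7.3 is unknown. The conclusion does not rest on these figures. It rests on the literal reading of 7.3 and on adverse events being held in the CRF. It is a cheap improvement worth making.

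**What to change.** Amend section 7.3 and the matching information sheet and consent wording as follows.

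1. Add an option under which a participant who stops study product continues the 3- and 6-month assessments, at minimum the 6-month PINP sample and the adverse event review. This concerns follow-up only and sets no rule on when product is stopped.
2. Retain data already collected, including adverse events and allocation, for every withdrawal. Limit destruction on request to stored samples. Section 9.2 stores serum before central analysis, so the text should also say what happens to serum not yet assayed for PINP.
3. Reconcile 7.3 with 13.2, 13.3 and 16.4, so that a site can follow all four for the same participant.

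How the retained values are analysed is a matter for the statistical analysis plan and is not part of this point.

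The cost is one text amendment with its approvals. The real downside is that a participant can no longer have already-collected data erased, and the consent documents must say so plainly. Anyone already enrolled under the present promise needs separate consideration.

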8. STUDY ASSESSMENTS

8.1 Baseline visit

At the baseline visit, information will be collected on past medical history, current medications and medications taken during the previous 3 months. Diet will be assessed using a validated food frequency questionnaire (the Scottish Collaborative Group FFQ). Smoking and alcohol intake will be recorded.

The sites of Paget's disease will be recorded based on review of the medical records and the results of imaging. Analysis. The presence and severity of bone pain localised to sites affected by PDB will be recorded using a visual analogue scale with ratings from 0 (no pain) to 10 (the worst pain possible). Health related quality of life including bodily pain assessed by SF36 will also be recorded

A blood sample will be taken for routine biochemistry and haematology and sent to the local laboratory for analysis. An additional blood samples will be taken for analysis of specialised markers of bone metabolism, for genetic and epigenetic analysis and for transcriptome analysis. A stool and saliva sample will be obtained for analysis of the microbiome.

Following randomisation, participants will be given 3-month's supply of the intervention (probiotic, placebo or calcium and vitamin D supplement). Participants randomised to receive the probiotic or placebo will be advised that they should store the supplement in a refrigerator during the study. Participants randomised to the calcium and vitamin D supplements will be advised that the supplements should be stored at room temperature.

